## SUBJECT POPULATION

### Key Inclusion Criteria

- Subjects must be 18 to 70 years of age, inclusive.
- Subjects must have CHB infection documented by:
  - Serum HBsAg-positive at screening and serum HBsAg- or HBV DNA-positive at least 6 months prior to screening;
  - Serum immunoglobulin M (IgM) anti-HBc antibody negative at screening.
- In subjects currently not being treated (Treatment Arms 1-2-3 and 6-7-8):
  - Subjects must not be receiving any CHB treatment at screening, ie,
    - Have never received treatment with HBV antiviral medicines, including NAs or interferon (IFN) products, OR
    - Have not been on treatment with HBV antiviral medicines, including NAs or IFN products, within 6 months prior to baseline (first intake of study drugs), AND
  - Subjects must be HBeAg-positive and have HBV DNA  $\geq 20,000$  IU/mL, OR be HBeAg-negative and have HBV DNA  $\geq 2,000$  IU /mL at screening, AND
  - Subjects must have HBsAg  $> 250$  IU/mL at screening, AND
  - Subjects must have ALT  $>$  upper limit of normal (ULN) and  $\leq 5 \times$  ULN at screening, determined in the central laboratory.

**Note:** If subjects were treated with investigational anti-HBV agents more than 6 months before screening, the sponsor should be contacted to discuss the case. Subjects who have received treatment with a CAM for more than 4 weeks any time prior to screening are excluded.

- In virologically suppressed subjects (Treatment Arms 4-5 and 9-10):
  - Subjects must be virologically suppressed by current NA treatment (ETV or TDF) as defined by HBV DNA <60 IU/mL at screening and at least 6 months prior to screening, AND
  - Subjects must be on the same NA treatment (ETV or TDF) and the same dose for  $\geq 12$  months prior to screening, AND
  - Subjects must have HBsAg >250 IU/mL at screening, AND
  - Subjects must have ALT  $\leq 2$ x ULN at screening.

**Note:** If subjects were treated with investigational anti-HBV agents more than 6 months before screening, the sponsor should be contacted to discuss the case. Subjects who have received treatment with a CAM for more than 4 weeks any time prior to screening are excluded.

**Note:** The current NA treatment can either be a branded product or a locally approved generic alternative (including different salt forms [eg, tenofovir maleate or succinate]). During the study, subjects will receive branded ETV (Baraclude®) or TDF (Viread®) treatment, as applicable.

- Subjects must have:
  - A liver biopsy result classified as Metavir F0-F2 within 1 year prior to screening or at the time of screening, OR
  - FibroScan™ liver stiffness measurement <8.0 kPa within 6 months prior to screening or at the time of screening.

### Key Exclusion Criteria

- Subjects who test positive for anti-HBs antibodies.
- Subjects with current hepatitis A virus infection (confirmed by hepatitis A antibody IgM), hepatitis D virus (HDV) infection (confirmed by HDV antibody), hepatitis E virus infection (confirmed by hepatitis E antibody IgM), or human immunodeficiency virus type 1 (HIV-1) or HIV-2 infection (confirmed by antibodies) at screening; subjects with a history of or current HCV infection (confirmed by HCV antibody). Evidence of other active infection (bacterial, viral, fungal, including acute tuberculosis) deemed clinically relevant by the investigator that would interfere with study conduct or its interpretation will also lead to exclusion.
- Subjects with any evidence of hepatic decompensation at any time point prior to or at the time of screening:
  - Direct bilirubin >1.2x ULN, or
  - International normalized ratio >1.5x ULN, or
  - Serum albumin < lower limit of normal (LLN), or
  - Documented history or current evidence of variceal bleeding, ascites, or hepatic encephalopathy.
- Subjects with any evidence of liver disease of non-HBV etiology. This includes but is not limited to hepatitis virus infections mentioned above, drug- or alcohol-related liver disease, autoimmune hepatitis, hemochromatosis, Wilson's disease, Gilbert's syndrome,  $\alpha$ -1 antitrypsin deficiency, primary biliary cirrhosis, primary sclerosing cholangitis, or any other non-HBV liver disease considered clinically significant by the investigator.
- Subjects who have signs of hepatocellular carcinoma (HCC) on an abdominal ultrasound performed within 2 months prior to screening or at the time of screening. In case of suspicious findings on

conventional ultrasound the subject may still be eligible if HCC has been ruled out by a more specific imaging procedure (contrast enhanced ultrasound, computed tomography [CT] or magnetic resonance imaging [MRI]).

- Subjects who have received an organ transplant.

## **DOSAGE AND ADMINISTRATION**

Study drugs (JNJ-56136379/NA/placebo) will be administered orally. JNJ-56136379 will be provided as 25-mg and/or 100-mg tablets and placebo as matching tablets. Subjects should be instructed to take JNJ-56136379/placebo in the morning at approximately the same time each day, together with breakfast. The tablets should be swallowed as a whole. At each study visit, the study drug should be taken on site under the supervision of the study staff. The time of study drug intake should be recorded in the eCRF.

A subject diary will be provided to the subjects undergoing semi-rich pharmacokinetic sampling and 24-hour urine sampling (pharmacokinetic subgroup), and female subjects using hormonal contraceptives. These subjects should report the times of study drug intake at home for 1 week prior to their Week 12 and Week 24 visits in this diary.

Subjects will receive commercially available Baraclude® (ETV) or Viread® (TDF) during the study (will be provided through this study), as applicable. Subjects who are already being treated with Baraclude® or Viread® at screening, will continue this NA treatment. Subjects will be switched to these branded NA treatments for the course of the study in case they are on another originator branded or a generic ETV or TDF treatment, respectively, at screening.

For subjects who are not receiving any CHB treatment at screening, the choice of NA (ETV or TDF) will be at the investigator's discretion, as per local practice. However, subjects with any NA treatment experience prior to screening, should be treated with TDF. In case the investigator's preference is to start ETV treatment in subjects with prior ETV experience without evidence of resistance, the sponsor should be contacted to agree on the NA to be used in the study.

NA (ETV or TDF) will be taken as per the package insert (Baraclude® and Viread®, respectively). In the event of decline in renal function, dosing interval for ETV or TDF may be adjusted as per the package insert.

## Description of Interventions

### Treatment Overview

Treatment	Dosing Regimen	Part A	
			Formulation
Subjects currently not being treated:			
Arm 1 e	75 mg JNJ-56136379 once daily (open-label)		3 x 25-mg tablets of JNJ-56136379 a
Arm 2	Matching placebo + NA (0.5 mg ETV or 300 mg TDF) once daily		3 tablets of matching placebo + 1 tablet of ETV b or TDF c
Arm 3	75 mg JNJ-56136379 + NA (0.5 mg ETV or 300 mg TDF) once daily		3 x 25-mg tablets of JNJ-56136379 + 1 tablet of ETV or TDF

### Virologically suppressed subjects:

Treatment	Dosing Regimen	Formulation
Subjects currently not being treated:		
Arm 4	Matching placebo + NA (0.5 mg ETV or 300 mg TDF) once daily	3 tablets of matching placebo + 1 tablet of ETV or TDF
Arm 5	75 mg JNJ-56136379 + NA (0.5 mg ETV or 300 mg TDF) once daily	3 x 25-mg tablets of JNJ-56136379 + 1 tablet of ETV or TDF

Treatment	Dosing Regimen	Part B	
			Formulation
Subjects currently not being treated:			
Arm 6	250 mg JNJ-56136379 d once daily (open-label) from Day 1 to Week 24 f	2 x 100-mg and 2 x 25-mg tablet(s) of JNJ-56136379 from Day 1 to Week 24	
	250 mg JNJ-56136379 d + NA once daily (open-label) from Week 24 to Week 48	2 x 100-mg and 2 x 25-mg tablet(s) of JNJ-56136379 + 1 tablet of ETV or TDF from Week 24 to Week 48	
Arm 7	Matching placebo + NA (0.5 mg ETV or 300 mg TDF) once daily	Tablet(s) of matching placebo + 1 tablet of ETV or TDF	
Arm 8	250 mg JNJ-56136379 d + NA (0.5 mg ETV or 300 mg TDF) once daily	2 x 100-mg and 2 x 25-mg tablet(s) of JNJ-56136379 + 1 tablet of ETV or TDF	
Virologically suppressed subjects:			
Arm 9	Matching placebo + NA (0.5 mg ETV or 300 mg TDF) once daily	Tablet(s) of matching placebo + 1 tablet of ETV or TDF	
Arm 10	250 mg JNJ-56136379 d + NA (0.5 mg ETV or 300 mg TDF) once daily	2 x 100-mg and 2 x 25-mg tablet(s) of JNJ-56136379 + 1 tablet of ETV or TDF	

a JNJ-56136379 is formulated as 25-mg (G008) and 100-mg (G009) tablets (matching placebo: G010 and G011, respectively).

b ETV (Baraclude®) is formulated as 0.5-mg film-coated tablets (commercially available), and is to be taken on an empty stomach. Lamivudine-refractory subjects should be treated with TDF instead.

c TDF (Viread®) is formulated as 300-mg film-coated tablets (commercially available), and is to be taken with food.

d The dose for Part B has been selected based on all safety, PK, and antiviral activity data available upon completion of the highest JNJ-56136379 dose group (who received 250 mg once daily) in the Phase 1 study 56136379HPB1001 in treatment-naïve CHB-infected subjects treated for 28 days.

e Treatment Arm 1 was discontinued early per Protocol Amendment 4. All subjects were to stop further dosing with JNJ-5613379 75 mg, start treatment with NA, and enter the post-treatment follow-up phase (Schedule 1).

f Per protocol Amendment 4, a futility rule has been installed: if  $\geq 1$  subject in the 250 mg monotherapy arm experiences virological breakthrough during the first 24 weeks of treatment, NA treatment will be added to JNJ-56136379 treatment as soon as possible for all remaining subjects.

## EFFICACY EVALUATIONS

Qualitative and quantitative HBsAg and HBeAg, and quantitative HBcrAg as well as anti-HBs and anti-HBe antibodies will be determined using standard serologic assays in a central laboratory. Samples for the determination of HBsAg and HBeAg will be processed in real-time using an assay such as the ARCHITECT platform (Abbott Laboratories). Samples for the determination of HBcrAg can be analyzed in batch and at the sponsor's discretion.

HBV DNA and HBV RNA will be quantified at a central laboratory using in vitro nucleic acid amplification tests for the quantification of HBV DNA and HBV RNA. Samples for the determination of HBV DNA will be processed in real-time using a test such as the COBAS® TaqMan® HBV Test, v2.0 (Roche Molecular Systems). Samples for the determination of HBV RNA can be analyzed in batch and at the sponsor's discretion.

Post-baseline results from HBsAg, HBeAg, anti-HBs, and anti-HBe antibody testing will be provided to the investigator and the sponsor from Week 20 onwards. HBV DNA results will be provided to the investigator and the sponsor from screening until FU Week 24 or 48, as applicable. It is the responsibility of the investigator:

- To monitor HBV DNA results and ensure that JNJ-56136379 treatment is discontinued in subjects with viral breakthrough and in treatment-naïve subjects with  $<1 \log_{10}$  IU/mL decline from baseline at Week 4 and Week 8 (Section 10.2 of the protocol)
- To monitor HBV DNA to assess if treatment extension criteria (Section 6.1 of the protocol) are met
- To assess if treatment completion criteria (Section 6.2 of the protocol) are met
- To assess whether re-start of NA treatment during follow up is needed (Section 6.3 of the protocol).

Viral genome sequence analysis will be performed to identify pre-existing baseline polymorphisms and to evaluate emergence of mutations associated with JNJ-56136379 and/or ETV or TDF treatment.

In subjects from the pharmacokinetic subgroup and subjects enrolled at a site with an on-site Fibroscan device, Fibroscan assessments will be performed to determine changes in fibrosis.

Samples may be used by the sponsor for additional exploratory assessments analyzing the serologic and virologic characteristics of HBV infection and efficacy or safety of the study treatment, including viral genotypic and phenotypic assessments.

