## 3. STUDY DESIGN AND RATIONALE

### 3.1. Overview of Study Design

This is a multicenter, interventional, randomized, partially-blind, placebo-controlled, two-part study to assess the efficacy, safety, and pharmacokinetics of treatment with two doses of JNJ-56136379 administered as monotherapy and in combination with NA (either ETV or TDF as per local practice) in HBeAg-positive and -negative CHB-infected subjects. Subjects who completed the initial 24 weeks of treatment with a virologic response by Week 20 (HBV DNA  $<200$  IU/mL of the HBV DNA assay) and without experiencing any safety concerns precluding continued study drug treatment as determined by the investigator, will continue study drugs up to 48 weeks in a treatment extension phase.

The study will initially consist of 2 parts, Part A and Part B. For each part, a sample size of 110 subjects is targeted who will receive JNJ-56136379 at two dose levels as monotherapy or in combination with an NA. Additional parts may be added through a protocol amendment based on emerging data.

Each part will consist of 2 types of CHB-infected subject populations: (1) subjects who are currently not being treated for their CHB infection (including CHB treatment-naïve subjects) and (2) subjects virologically suppressed by current NA treatment (either ETV or TDF as per local practice).

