### **4.1. Inclusion Criteria**

Each potential subject must satisfy all of the following criteria to be enrolled in the study:

1. Subjects must be 18 (or older legal age of consent as per local requirements) to 70 years

of age, inclusive.

2. Subjects must have a body mass index (weight in kg divided by the square of height in meters) of 18.0 to 35.0 kg/m^2, extremes included.
3. Criterion modified per Amendment 3
  - 3.1. Subjects must have CHB infection documented by:
    - Serum HBsAg-positive at screening and serum HBsAg- or HBV DNA-positive at least 6 months prior to screening;
    - Serum immunoglobulin M (IgM) anti-HBc antibody negative at screening.
4. In subjects currently not being treated (Treatment Arms 1-2-3 and 6-7-8):
  - a. Subjects must not be receiving any CHB treatment at screening, ie,
    - Have never received treatment with HBV antiviral medicines, including NAs or IFN products, OR
    - Have not been on treatment with HBV antiviral medicines, including NAs or IFN products within 6 months prior to baseline (first intake of study drugs), AND
  - b. Subjects must be HBeAg-positive and have HBV DNA  $\geq$ 20,000 IU/mL, OR be HBeAg-negative and have HBV DNA  $\geq$ 2,000 IU /mL at screening, AND
  - c. Subjects must have HBsAg  $>$ 250 IU/mL at screening, AND
  - d. Subjects must have ALT  $>$  upper limit of normal (ULN) and  $\leq$ 5 x ULN at screening, determined in the central laboratory.
- Note:** If subjects were treated with investigational anti-HBV agents more than 6 months before screening, the sponsor should be contacted to discuss the case. Subjects who have received treatment with a CAM for more than 4 weeks any time prior to screening are excluded.
5. Criterion modified per Amendment 3
  - 5.1. In virologically suppressed subjects (Treatment Arms 4-5 and 9-10):
    - a. Subjects must be virologically suppressed by current NA treatment (ETV or TDF) as defined by HBV DNA  $<$ 60 IU/mL at screening and at least 6 months prior to screening, AND
    - b. Subjects must be on the same NA treatment (ETV or TDF) and the same dose for  $\geq$ 12 months prior to screening, AND
    - c. Subjects must have HBsAg  $>$ 250 IU/mL at screening, AND
    - d. Subjects must have ALT  $\leq$ 2x ULN at screening.

**Note:** If subjects were treated with investigational anti-HBV agents more than

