## 6. DOSAGE AND ADMINISTRATION

The subjects will receive the treatments as described in [Table 4](#). Study drugs (JNJ-56136379/NA/placebo) will be administered orally.

JNJ-56136379 will be provided as 25-mg and/or 100-mg tablets and placebo as matching tablets. Subjects should be instructed to take JNJ-56136379/placebo in the morning at approximately the same time each day, together with breakfast. The tablets should be swallowed as a whole. At each study visit, the study drug should be taken on site under the supervision of the study staff. The time of study drug intake should be recorded in the eCRF.

A subject diary will be provided to the subjects undergoing semi-rich pharmacokinetic sampling and 24-hour urine sampling (pharmacokinetic subgroup), and female subjects using hormonal contraceptives. These subjects should report the times of study drug intake at home for 1 week prior to their Week 12 and Week 24 visits in this diary. To ensure compliance, the investigator or study-site personnel will review the recorded data in the subject's diary.

Subjects who are already being treated with ETV or TDF at screening, will continue NA treatment which will be provided through this study. Subjects will receive Baraclude® (ETV) or Viread® (TDF) during the study, as applicable. Subjects will be switched to these branded NA treatments for the course of the study in case they are on another originator branded or a generic ETV or TDF treatment, respectively, at screening.

For subjects who are not receiving any CHB treatment at screening, the choice of NA (ETV or TDF) will be at the investigator's discretion, as per local practice. However, subjects with any NA treatment experience prior to screening, should be treated with TDF. In case the investigator's preference is to start ETV treatment in subjects with prior ETV experience without evidence of resistance, the sponsor should be contacted to agree on the NA to be used in the study.

NA (ETV or TDF) will be taken as per the package insert (Baraclude® and Viread®, respectively). In the event of decline in renal function, dosing interval for ETV or TDF may be adjusted as per the package insert.

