## 7. TREATMENT COMPLIANCE

All study drug intakes at the study site must be witnessed by the investigator or by study-site personnel dedicated to the study.

For intake of study drugs at home, the subjects in the pharmacokinetic subgroup should report the times of intake of study drug for 1 week prior to their Week 12 and Week 24 visits in a subject diary which will be provided for this purpose.

The subjects will be requested to bring unused study drugs and empty packaging to the study site at each visit.

Every effort should be made to have the subject take the study drugs as indicated in the [TIME AND EVENTS SCHEDULE](#), especially in subjects who have previously been treated. In case a dose of JNJ-56136379 was missed, the dose should be given as soon as possible but within 12 hours after the scheduled time. Otherwise, the dose should be skipped and the next dose should be given at the next scheduled time point per the initial dosing schedule. If more than 3 subsequent doses are missed, the investigator should be contacted and the case should be discussed with the sponsor. If a dose of NA is missed, the subject should follow the guidelines in the package insert.

If a subject's drug intake is not according to the protocol, the investigator will take the necessary measures to ensure future adherence to the protocol.

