### **9.2. Efficacy Evaluations**

Efficacy assessments will be performed at the time points indicated in the [TIME AND EVENTS SCHEDULE](#).

Qualitative and quantitative HBsAg and HBeAg, and quantitative HBcrAg as well as anti-HBs and anti-HBe antibodies will be determined using standard serologic assays in a central laboratory. Samples for the determination of HBsAg and HBeAg will be processed in real-time using an assay such as the ARCHITECT platform (Abbott Laboratories). Samples for the determination of HBcrAg can be analyzed in batch and at the sponsor's discretion.

HBV DNA and HBV RNA will be quantified at a central laboratory using in vitro nucleic acid amplification tests for the quantification of HBV DNA and HBV RNA. Samples for the determination of HBV DNA will be processed in real-time using a test such as the COBAS® TaqMan® HBV Test, v2.0 (Roche Molecular Systems). Samples for the determination of HBV RNA can be analyzed in batch and at the sponsor's discretion.

Post-baseline results from HBsAg, HBeAg, anti-HBs, and anti-HBe antibody testing will be provided to the investigator and the sponsor from Week 20 onwards. HBV DNA results will be provided to the investigator and the sponsor from screening until FU Week 24 or 48, as applicable. It is the responsibility of the investigator:

- To monitor HBV DNA results and ensure that JNJ-56136379 treatment is discontinued in subjects with viral breakthrough and in treatment-naïve subjects with  $<1 \log_{10}$  IU/mL decline in HBV DNA from baseline at Week 4 and Week 8 (see Section 10.2)
- To monitor HBV DNA to assess if treatment extension criteria (see Section 6.1) are met
- To assess if treatment completion criteria (see Section 6.3) are met
- To assess whether re-start of NA treatment during follow-up is needed (see Section 6.4).

In subjects from the pharmacokinetic subgroup and subjects enrolled at a site with an on-site Fibroscan device, Fibroscan assessments will be performed to determine changes in fibrosis.

The blinded data collected from baseline onwards will be provided to the investigator at the end of the study to complete the subject's medical records.

Samples may be used by the sponsor for additional exploratory assessments analyzing the serologic and virologic characteristics of HBV infection and efficacy or safety of the study treatment.

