10. The subject has a QTcF prolongation (defined as a QTcF value of  $>500$  ms, or an increase from baseline of  $>60$  ms) at any given time point (confirmed by repeat ECG).
11. The subject has at Week 4  $<1 \log_{10}$  IU/mL decline in HBV DNA from baseline, confirmed by retesting at the Week 8 visit (treatment-naïve only).
12. The subject has confirmed HBV virological breakthrough (ie, confirmed on-treatment HBV DNA increase by  $>1 \log_{10}$  IU/mL from nadir level or confirmed on-treatment HBV DNA level  $>200$  IU/mL in subjects who had HBV DNA level  $<$  LLOQ of the HBV DNA assay).
13. The subject requires treatment with any of the disallowed medications listed in Section 8.

Retesting for confirmation of the above-mentioned abnormal safety parameters (ie, not applicable to criteria 11 and 12 listed above) should take place within 72 hours after the initial results become available and may require an unscheduled visit.

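### The Week 4/8 HBV DNA non-response stop covers treatment-naïve subjects only, so a previously treated non-responder can stay on JNJ-56136379 until Week 24 (minor; few if any subjects affected)

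*Protocol*

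**What the plan says.** **The stop rule.** The synopsis (Efficacy Evaluations) asks the investigator to ensure that "JNJ-56136379 treatment is discontinued in subjects with viral breakthrough and in treatment-naïve subjects with" less than 1 log10 IU/mL decline. Protocol 9.2 repeats this, with the threshold applied to the "decline in HBV DNA from baseline at Week 4 and Week 8 (see Section 10.2". In 10.2, criterion 11 requires the Week 4 result to be "confirmed by retesting at the Week 8 visit (treatment-naïve only".

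**The population.** Protocol 3.1 defines the first study population as "subjects who are currently not being treated for their CHB infection (including CHB treatment-naïve subjects", so treatment-naïve is a subset. Criterion 4a in 4.1 admits never-treated subjects or, as the alternative, those who "Have not been on treatment with HBV antiviral medicines, including NAs or IFN products within 6 months prior to baseline". Section 6 plans for the second group in the untreated arms: "subjects with any NA treatment experience prior to screening, should be treated with TDF". Section 7 stresses adherence "especially in subjects who have previously been treated", although that phrase may also cover the virologically suppressed arms.

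**The neighbouring rules.**
- Criterion 12 applies to everyone: "The subject has confirmed HBV virological breakthrough (ie, confirmed on-treatment HBV DNA increase by" more than 1 log10 from nadir, or a confirmed level above 200 IU/mL after having been below LLOQ.
- Criterion 2 lets the investigator stop treatment, but is worded for safety or tolerability.
- Section 6.2 adds an NA for all remaining Arm 6 subjects once any one of them has a virological breakthrough.
- Section 6.1 requires HBV DNA below 200 IU/mL by Week 20 for extension beyond Week 24.

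**The SAP.** Section 5.3 limits the matching limb of on-treatment failure in the Week 24 period to the naïve population.

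**The concern.** Two subjects in the same arm with the same HBV DNA course are handled differently. The treatment-naïve subject must stop JNJ-56136379 once Week 8 confirms the poor Week 4 response. The previously treated subject need not, and the protocol gives no reason for the difference.

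The stakes are mainly in Arm 6. Arm 1 has been closed, Arms 2 and 7 receive no JNJ-56136379, and Arms 3 and 8 also receive an NA. A non-responder on 250 mg monotherapy would go without effective treatment. Protocol 3.1 justifies having no placebo control for monotherapy by saying that these subjects are eligible for treatment and should not go without it. For monotherapy subjects, stopping early is also what leads to starting an NA.

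**Working it through.** The plan states no figure on this point, so the check is whether any other individual rule catches a previously treated subject whose HBV DNA stays less than 1 log10 below baseline.

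**Inputs.** Screening minima are 2,000 IU/mL (HBeAg-negative) and 20,000 IU/mL (HBeAg-positive), from 4.1. LLOQ is 20 IU/mL, from SAP 5.1. Assumption: baseline is not below the screening minimum.

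1. **Criterion 12, LLOQ limb.** Reaching LLOQ takes a decline of log10(2,000/20) = 2.0 or log10(20,000/20) = 3.0. With less than 1 log10 decline the subject never gets there, so this limb cannot apply.

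2. **Criterion 12, nadir limb.** With decline d at nadir, a rise of more than 1 log10 means HBV DNA above 10^(1−d) × baseline:
   - d = 0.9: above 1.26 × baseline
   - d = 0.5: above 3.16 × baseline
   - d = 0: above 10 × baseline

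   Since d is below 1, the subject must always rise above baseline. A flat course does not trigger it.

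3. **Other individual stops.** Criterion 2 does not name lack of response. The scheduled Week 12 and Week 16 HBV DNA results carry no non-response action.

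4. **Week 20 extension criterion.** A decline below 1 log10 leaves HBV DNA above 2,000/10 = 200 IU/mL or above 20,000/10 = 2,000 IU/mL. The subject fails the 200 IU/mL threshold, and JNJ-56136379 ends at Week 24.

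5. **Extra exposure.** Week 24 − Week 8 = up to 16 weeks.

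Applying criteria 11 and 12 and the Week 20 check to flat courses from 2,000, 20,000 and 10,000,000 IU/mL, and to a constant 0.9 log10 decline from each, gives the same answer. As written, the previously treated subject meets neither criterion 11 nor criterion 12 and fails only at Week 20. With criterion 11 widened, the subject meets it at Week 8 in every case.

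**How many subjects.** The documents do not give the share of previously treated subjects or their non-response rate. For Arm 6 (planned N = 30), with an assumed share of 10% to 50% and an assumed non-response rate of 1% to 5%:
- Expected number: 30 × 0.10 × 0.01 = 0.03, up to 30 × 0.50 × 0.05 = 0.75.
- Chance of at least one: 1 − (1 − 0.001)^30 = 3%, up to 1 − (1 − 0.025)^30 = 53%.

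The only related data are for treatment-naïve Phase 1 subjects at 250 mg (protocol 1.1): a mean Day 29 decline of 2.70 log10 with SD 0.33. The threshold therefore lies (2.70 − 1.00)/0.33 = 5.2 SD below the mean, which points to the low end of the range if previously treated subjects respond similarly.

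**The case against.** The strongest reply is that the limit is written identically in three protocol places and mirrored in SAP 5.3. It is then either a deliberate scope or loose wording. SAP 2.5 does write treatment naïve for the stratum that SAP 4.2.2 and 4.2.3 call currently not treated. That may explain the origin, but the protocol itself keeps the two terms apart, and an investigator follows the protocol.

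Several stronger readings are tempting, and the documents do not support them.

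- **That the subject is left without any safeguard.** HBV DNA is processed in real time and reported to investigator and sponsor, and the DRC reviews unblinded efficacy and safety data regularly. The Arm 6 futility rule can also help a subject who never breaks through, because one breakthrough in any Arm 6 subject adds an NA for the rest. If each of 30 subjects had an assumed, independent 1% to 5% breakthrough risk, the chance of a trigger would be 1 − 0.99^30 = 26% to 1 − 0.95^30 = 79%. Its timing is not guaranteed and it does not stop JNJ-56136379, but it would end monotherapy.
- **That a flat early response breeds resistance.** Protocol 1.3.4 links expected resistance to the observed breakthroughs, not to early non-response. It adds that resistant variants remain susceptible to NAs.
- **That the efficacy results are distorted, or that SAP and protocol conflict.** The primary HBsAg analysis in SAP 5.2.1.1 does not use the failure definition. SAP 5.3 already matches the protocol, and its Table 4 tabulates the Week 4/8 reduction with no naïve limit. The Week 48-period failure definition captures subjects who miss the extension criteria.

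One practical objection also stands in part. Arm 6 was already on treatment at Amendment 4 (20 February 2019). The SAP dates Amendment 5 at 2 August 2019, 163 days or about 23 weeks later, so those subjects were past Week 8. Whether Arm 6 enrolment continued is not stated, so the change may reach few subjects.

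**Conclusion.** The gap is real but minor, and it concerns a conduct rule rather than an analysis choice. Read as written, criterion 11 leaves a previously treated subject with a persistent decline below 1 log10 on JNJ-56136379 for up to 16 weeks longer than a naïve subject with the same course. No other individual non-response rule intervenes before Week 24.

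This rests on baseline HBV DNA not being below the screening minimum and on HBV DNA not rising enough above baseline to meet criterion 12. It matters in practice for Arm 6, where the issue is time without effective treatment. Few if any subjects are likely to be affected. A reader might take the 53% as a likely chance of an affected subject, but it is the top corner of an assumed range with no source in the documents.

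**What to change.** In the synopsis (Efficacy Evaluations), protocol 9.2 and protocol 10.2 criterion 11, replace *treatment-naïve* by *currently not being treated (Arms 1-3 and 6-8)*. Make the same change to the Week 24-period failure limb in SAP 5.3, so that it continues to match. The virologically suppressed arms stay outside the rule, as they should: they enter with HBV DNA below 60 IU/mL, where a 1 log10 decline is not a sensible test.

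The cost is a protocol amendment with IEC/IRB approval (protocol 17.1), because a mandatory discontinuation criterion is widened, and possibly a few more early discontinuations. No new data are needed: HBV DNA at Weeks 4 and 8 is already scheduled. No sample size or power figure changes.
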